Randomization: Subjects in each of the two age groups (5-17 and ≥ 18 years of age) will be randomized to either the dexamethasone or placebo group (0.3 mg/kg every 12 hours x 4 doses, then tapered). Randomization will be stratified by site, age group, and severity of ACS to preserve balance across treatment groups.

Title of the Protocol: Randomized Trial of Oral Dexamethasone for Acute Chest Syndrome

Data Analyses: We will evaluate the difference in duration of symptoms for ACS between the two treatment groups using a generalized linear mixed model (GLMM). Here, the natural log of the duration of symptoms will act as the dependent variable of interest and the treatment status as the grouping factor. As a secondary analysis, the duration of hospitalization, supplemental oxygen, and fever will be analyzed in a similar manner. Laboratory parameters will be analyzed using a GLMM model, with treatment group, baseline laboratory value, age group, severity, and site as fixed effects and subject as a random effect. Clinical endpoints and AEs will be summarized by treatment and analyzed for differences across treatment group. Two formal interim analyses will be performed on the primary efficacy variable. The first interim analysis will take place when 56 subjects have resolved signs and symptoms of ACS OR have been discharged from the hospital. In this interim analysis, the primary efficacy hypothesis will be tested at the $\alpha = 0.001$ level. The study will be stopped if significant efficacy is identified. The second interim analysis will be performed when 112 subjects have resolved signs and symptoms of ACS OR have been discharged from the hospital. The primary efficacy hypothesis will be tested at the $\alpha = 0.01$ level. If significant efficacy is identified for total subjects and for children, the study will be stopped. Otherwise, the study will continue enrollment to 112 children, after which the primary efficacy hypothesis will be tested on the $\alpha = 0.039$ level.

Human Subjects: Potential risks include avascular necrosis, vaso-occlusive crisis, mood changes, hypertension, nausea, vomiting, dyspepsia, gastric ulceration, delayed wound healing, acne, and infection.

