5 BACKGROUND AND RATIONALE

Introduction: SCD is a chronic disorder caused by a mutant hemoglobin. The substitution of the amino acid valine by glutamic acid in the sixth position of the beta subunit of hemoglobin produces sickle hemoglobin (Hgb S). This mutation promotes the hydrophobic interaction and polymerization of deoxygenated Hgb S molecules, producing rigid, elongated red blood cells (RBCs), or sickle cells, that obstruct the microcirculation. The gene for Hgb S arose in historically malarious regions of the world because the heterozygous state offered protection against the malaria parasite, and the gene is now found in individuals of African, Arabic, Hispanic, Greek, and Italian descent. The gene frequency of Hgb S is particularly high in individuals of African ancestry in the United States, among whom 9% are heterozygotes. SCD occurs in individuals who are homozygous for Hgb S or are compound heterozygotes for Hgb S and certain other abnormal hemoglobins. Approximately 1 in 600 African-Americans has SCD and at least 60,000 individuals are affected in the United States.¹ SCD is characterized by chronic anemia and episodic “vaso-occlusive” crises. Acute pulmonary disease, descriptively termed “acute chest syndrome” (ACS),² is one of these events.

Acute Chest Syndrome: ACS is defined clinically as a new pulmonary radiographic infiltrate and concurrent signs and symptoms of acute pulmonary disease.^{3,4} Fever and cough are common clinical findings in young children with ACS, but chest pain, shortness of breath, chills, a productive cough, and hemoptysis are more common in older individuals. About two-thirds of patients with ACS are hypoxemic, and most have an acute 1 to 2 g/dL decrease in hemoglobin concentration. The signs and symptoms of ACS may precede the appearance of an infiltrate on a chest radiograph. Lower and middle lobes are affected more often than upper lobes in adults, although upper lobe disease is more common in children. Bilateral infiltrates or involvement of multiple lobes predicts severe disease.

Significance: ACS is a common cause of hospitalization for patients with SCD, second only to painful crisis.^{5,6} This complication is not always apparent at the time of admission to the hospital, however. Patients may have fever or acute pain, especially in

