8.1 Inclusion Criteria

Subjects who meet all of the following criteria are eligible for enrollment into the study:

1. Age \geq 5 years;
2. Diagnosis of sickle cell anemia (Hgb SS) or sickle- β^0 -thalassemia (Hgb S β^0);

3. Current episode of ACS defined as a new lobar or segmental pulmonary infiltrate seen on a chest radiograph and two or more of the following findings in the 24 hours preceding enrollment (signing consent):
 - temperature $\geq 38.5^{\circ}\text{C}$,
 - tachypnea,
 - dyspnea or increased work of breathing,
 - chest wall pain, and
 - oxygen saturation of $< 90\%$ in room air by pulse oximetry;
4. Subjects must have one or more of the following findings at the time enrollment:
 - tachypnea,
 - dyspnea or increased work of breathing,
 - chest wall pain, and
 - oxygen saturation of $< 90\%$ in room air by pulse oximetry;
5. Current episode of ACS diagnosed within the preceding 24 hours;
6. Ability to take medication in capsule form;
7. Written, informed consent provided by the subject and/or parent(s) or guardian(s) before study entry.

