13.1 Analysis Populations

The general population will consist of hospitalized subjects 5 years of age and older with a diagnosis of SCD, who have experienced a current episode of ACS and who have provided a written informed consent. Randomized subjects who are not dosed will be replaced. Data collected on subjects who do not complete the study will be used whenever possible. The exact criteria used to establish each analysis population and any predefined reasons for eliminating subjects will be identified and documented before the study is unblinded.

Intent-to-Treat (ITT) / Safety population: All randomized subjects will be included in the ITT/Safety population. Subjects in the ITT population will be classified according to the treatment group to which they were randomized regardless of what study drug they received.

Per-Protocol population: The per-protocol population consists of all subjects from the ITT/Safety population who had no major protocol violations and who were followed until discharge from the study.

All analyses will be performed on the ITT population. Efficacy analyses will be repeated on the per protocol population.

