13.2.2 Efficacy Analyses

All efficacy analyses will be performed on the ITT population while the primary and some secondary analyses will be repeated on the per-protocol population. Center will be included in the models as permitted by sample size. Center will be eliminated from the models if it appears to be an insignificant variable in the model.

The primary analysis will compare the duration of ACS signs and symptoms (as assessed by the ACS assessment, Appendix3) or the duration of hospitalization for ACS, whichever happens first, of subjects in the dexamethasone treated arm to those in the placebo treated arm. The symptom/hospitalization duration for subjects with ACS will be summarized by treatment group, severity strata, and age strata. The effect of treatment on symptom/hospitalization duration will be tested using a Generalized Linear Mixed Model (GLMM) with the natural log of symptom/hospitalization duration as the outcome variable. The SAS[®] procedure MIXED will be used to fit the GLMM. The GLMM will include treatment, age group, and severity as fixed effects. The GLMM will not specify any variables as random effects or repeated effects, but it will use the GROUP option in the REPEATED statement to estimate separate error variances for each treatment (i.e., GROUP = “treatment”). The SAS[®] procedure MIXED will be used to fit the GLMM.

The GLMM model specified above is necessary for the primary analysis because pilot data give evidence that the length of stay (LOS) in the hospital (which is assumed to be similar to duration of symptoms) for ACS has a lognormal distribution. If the LOS for ACS is distributed as lognormal in each treatment group, then the model of the natural log of LOS must allow for differences in treatment group variances as well as for treatment group mean differences. By allowing for differences in treatment group variances and treatment group means, the treatment group specific distributions can be correctly estimated under the lognormal assumption, resulting in a correct comparison of treatment group means.

As a secondary analysis, parametric survival analysis techniques will be used to estimate distributional parameters and model the hazard function of symptom duration/LOS/hypoxemia/fever for each treatment group. The time to the event of interest (e.g., symptom duration) will be described using a Kaplan-Meier plot stratified by treatment.

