The effects of dexamethasone on secondary clinical endpoints of duration of hospitalization, supplemental oxygen therapy (or hypoxemia), and fever will be summarized by treatment group, severity strata, and age strata and evaluated by using a similar GLMM as the primary analysis. The secondary clinical endpoints of the amount of opioid usage, the number/type of transfusions, pulmonary function and pulmonary radiograph findings, the number of rebound hospitalizations, and pain scores, will be summarized by treatment group, severity strata, and age strata. The effects of dexamethasone treatment on these outcome variables will be evaluated using:

- GLMM with treatment, age group, severity, and timepoint as fixed effects and subject as a random effect for the longitudinal pain scores;
- Wilcoxon Rank test for rebound hospitalizations and number of transfusions;
- T-Test (or Wilcoxon Rank test if assumptions are not met) for the amount of opioid usage and all pulmonary function outcomes;
- Cochran-Mantel-Haenszel Chi-square test for radiographic findings (resolved, improved, unchanged, worse).

The secondary endpoints of the laboratory variables (VCAM₁, ICAM₁, P-selectin, L-selectin, vWF multimers, endothelial and monocyte microparticles, WBTF, NO, and sPLA₂) will be summarized by measurement timepoint, treatment group, severity strata, and age strata. The overall change from baseline for each of the collected measurements over time will be modeled using a random effects longitudinal mixed model, with treatment, baseline measurement, age group, and severity as fixed effects and subject as a random effect. This class of model allows us to control for the correlation induced by having multiple measurements on an individual. Estimates of the treatment difference over time will be depicted by displaying the estimated means of each treatment group over time. Descriptive p-values for comparisons of interest will also be produced.

All meaningful subject data collected in the CRFs will be provided in data listings. All statistical analyses will be performed using the SAS[®] System.

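### The log-duration model named for oxygen/hypoxemia and fever is undefined for subjects with zero duration, whom eligibility admits; dropping them is not ITT and hides any prevention effect.

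*Protocol*

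**What the plan says.** Section 13.2.2 defines the primary model as PROC MIXED "with the natural log of symptom/hospitalization duration as the outcome variable", with treatment, age group and severity as fixed effects and a separate error variance per arm. The same section states that durations of hospitalization, supplemental oxygen (or hypoxemia) and fever will be "evaluated by using a similar GLMM as the primary analysis". The Synopsis, directly after making log duration the dependent variable, adds: "As a secondary analysis, the duration of hospitalization, supplemental oxygen, and fever will be analyzed in a similar manner".

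The population is fixed as well. Section 13.2.2: "All efficacy analyses will be performed on the ITT population". Section 13.1: "All randomized subjects will be included in the ITT/Safety population".

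On who can be enrolled, section 8.1 asks for any two of five findings in the preceding 24 hours and any one of four at enrollment. Fever and saturation below 90% are options on the first list. The second list omits fever and keeps desaturation as an option. The Background (section 5) states: "About two-thirds of patients with ACS are hypoxemic". Section 9.1.5 ties supplemental oxygen to saturation.

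No rule for a zero duration is given.

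**The concern.** A subject who never has fever, desaturation or oxygen after the first dose has an observed duration of zero, the best possible outcome. The named model cannot use that value. PROC MIXED omits records with a missing response, so these subjects would leave the analysis without any decision having been taken.

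Three things follow. The stated model and the stated ITT population cannot both hold. Whether a subject has any oxygen need or fever after the first dose can depend on treatment, so comparing only those who do is no longer a randomized comparison. And a drug that works by preventing these events shows no effect in a model restricted to subjects who had them. Section 6.2 predicts decreases in oxygen use and in the durations of hypoxemia and fever, so this is the evidence for that secondary objective.

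The parametric survival models that section 13.2.2 plans for hypoxemia and fever likewise have no stated rule for times of zero.

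**Working it through.** **1. The plan's own figure.** Inputs from section 13.4: log means 4.25 and 3.95, log SDs 0.6 and 0.3, two-sided 0.05, 90% power.

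- Normal approximation: n = (1.960 + 1.282)² × (0.36 + 0.09) / 0.30² = 10.51 × 5 = 52.5, so 53 per arm.
- Satterthwaite t-test with the noncentral t: 54 per arm (power 0.901). This reproduces the stated 54. At 56 per arm the power is 0.91.
- Back-transformed means: exp(4.25 + 0.18) = 83.9 h and exp(3.95 + 0.045) = 54.3 h, a difference of 29.6 h against the stated 30 h.

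The log model does what it was designed for when every duration is positive. The protocol has no sizing figure for the oxygen or fever durations.

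**2. Subjects lost.** The share of zeros is an assumption. One-third is the complement of the Background figure for hypoxemia; the rest is a range. Dropped = 112 × share. The last column applies the primary endpoint's log effect and SDs to those left.

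| Zero share | Dropped of 112 | Left per arm | Power |
|---|---|---|---|
| 0 | 0 | 56 | 0.91 |
| 10% | 11 | 50 | 0.88 |
| 20% | 22 | 45 | 0.84 |
| one-third | 37 | 37 | 0.76 |
| 50% | 56 | 28 | 0.64 |

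**3. Effect on what can be detected.** Simulation with 56 per arm. Assumptions, none from the documents except the link to one-third: one-third zeros on placebo; positive durations lognormal with log mean 3.8 and SD 0.7. Three tests at 0.05: Welch t on log duration among positives; rank test on all subjects with zeros kept; and a two-part test that adds the squared statistic for the proportion with any duration to the squared statistic for log duration among positives, referred to chi-square on 2 df.

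| Scenario | Log model, positives only | Rank test, all | Two-part, all |
|---|---|---|---|
| Zeros 33% to 60%, same duration otherwise | 5% | 73% | 73% |
| Zeros 33% to 50%, same duration otherwise | 5% | 35% | 35% |
| Equal zeros, duration shorter by 0.3 log | 44% | 17% | 35% |

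With no effect at all, each test rejects about 5% of the time. In the first scenario the expected losses are 56 × 0.33 ≈ 19 on placebo and 56 × 0.60 ≈ 34 on dexamethasone, so the deletion itself differs by arm. The result does not need a large zero share: with zeros going from 15% to 35%, the log model has 5% power and the two-part test about 60%.

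**4. Adding a constant before taking logs.** A separate run used log mean 4.0, SDs 0.70 and 0.56 (close to the 2004 pilot study in Table 13.2) and ln(x + c) with c from 0.01 to 4 h. Power was 78% to 81% for a pure prevention effect (two-thirds against 40% with any duration). It was only 5% to 10% for a shortening of 0.26 log, that pilot's difference (4.216 − 3.954 = 0.262). On positives alone, the log model had 41% in that second case.

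**The case against.** The best defence is that the SAP, which is not shown, may settle this. The opening of section 13 defers detail to it and allows data transformations, and section 13.2.2 says similar rather than identical. That stands in part: a zero rule could be added there. But the protocol does more than stay silent. It names a model and a population that conflict for subjects it admits, and step 4 shows that a transformation alone is not a neutral repair. Section 13.3.5 does not help, since it deals with loss to follow-up, deaths and withdrawals, and a zero is an observed value.

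Other points stand:

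- A subject already on oxygen at the first dose has a positive duration whatever the drug does, so part of the split is set before treatment. The 33% to 60% scenario is therefore a strong prevention effect, not a forecast.
- For a pure duration effect, the planned model is the most powerful of the three.
- Section 13.2.2 also plans Kaplan-Meier plots and summaries by arm, which can display the zeros.

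A reader might infer more than the documents support:

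- That the analysis cannot be run. It can, on fewer subjects.
- That a third of trial subjects will have zero on all three endpoints. The only source is a general statement about hypoxemia in ACS, not about subjects after the first dose. It reaches oxygen only by inference from section 9.1.5. For fever, the protocol says only that it is common in young children.

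**Conclusion.** The point holds as a defect in a stated secondary analysis and should be fixed. Followed as written, the model for oxygen/hypoxemia and fever drops observed zero durations, compares a subset that treatment can alter, and is blind to prevention.

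The loss is about 11 to 56 of 112 subjects at zero shares of 10% to 50%, and about 37 at one-third. The power figures are illustrative and depend on the assumed zero shares and lognormal parameters. That the log model stays at its 5% null rate under pure prevention does not depend on those values: it follows from conditioning on positive durations whose distribution is the same in both arms.

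It would be wrong to infer that the trial's main result is at risk. The primary analysis, the interim boundaries and the sample size of 54 (56) per arm are untouched, and section 13.3.3 makes secondary p-values descriptive. A descriptive estimate from a treatment-dependent subset can still mislead.

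**What to change.** For supplemental oxygen, hypoxemia and fever, replace the single log model in section 13.2.2 by a two-part analysis of all randomized subjects:

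- (a) the proportion with any post-dose oxygen, hypoxemia or fever, in a logistic model with treatment, age group and severity;
- (b) the planned log model among those with a duration above zero, reported as a conditional comparison and not as an ITT effect;
- one 2-df test combining (a) and (b).

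Report the number of zeros by arm and state how zero times enter the parametric survival models. Keep the log model alone for duration of hospitalization. Align the Synopsis sentence.

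A simpler alternative is a rank test with zeros kept, which section 13.2.2 already uses for transfusions. It matches the two-part test under pure prevention but is weaker when only duration changes (17% against 35% in the example).

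The cost is wording and one extra model per endpoint. If zeros are unaffected by treatment, the two-part test gives up about 9 points of power against the log model (44% against 35%).

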9.2 Randomization and Masking

After enrollment, subjects will be randomized to one of two treatment arms. Subjects in Arm 1 will receive oral dexamethasone. Subjects in Arm 2 will receive oral placebo. A computer-generated, adaptive randomization schema will be used to allocate subjects 1:1 between the two treatment arms. Randomization will be stratified by site, age and the severity of ACS (see Section 8.3). In order to increase the likelihood of balance in treatment allocations, subjects will be randomized using the standardized range variation (79) of the sequential allocation algorithm of Pocock and Simon (80), a minimization method. This method attempts to achieve treatment balance on several subject characteristics (i.e. age group, site, and severity of ACS in this study) simultaneously – not within separate strata. Minimization consists of biasing the treatment allocation so as to minimize the total imbalance between the treatment groups on some scale (81). The order of entry of the subjects to the various centers and in the various prognostic groups is assumed to be random. As minimization is a dynamic method that uses information on subjects already entered to allocate treatment to the next subject, a continuous updating of the information related to previous treatment allocations is required, thus a centralized randomization system will be used.

Pharmacists at each center will be unblinded and will utilize information from the interactive voice/web randomization system (IVRS) at the SDMC to obtain a new treatment assignment for a subject and provide each subject with appropriate dosing of both therapies. The IVRS system has the capability of providing unblinding information in case of a medical emergency where the exact study drug is needed in order to appropriately treat a subject.

The time interval between Randomization and the first dose of study drug administration will be no longer than 2 hours. In the event a subject's first dose occurs outside the 2-hour time limit, the subject will still be included in the study and the analysis. This is in the spirit of the intention-to-treat analysis. The amount of time in excess of the 2-hour limit until the first dose of study drug will also be recorded. This event will be documented as a protocol deviation.

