10.3 Evaluations by Study Visit

10.3.1 Baseline Evaluations

A chest radiograph is necessary for the diagnosis of ACS, the medical care of the subject, and study enrollment. Immediately after enrolling a subject, the elements of the ACS assessment will be assessed and the following additional assessments performed or measurements taken: history (which includes the collection of any transfusions within 24 hours of enrollment), physical exam, vitals signs (includes blood pressure monitoring), a CBC, blood culture (for those subjects with fever), a pregnancy test if applicable, pain intensity (by Oucher or numeric rating scale), and peripheral oxygen saturation (by pulse oximetry) [See Table 10.2.] Additionally, a blood sample will be drawn for the central laboratory measurements (see Table 10.1).

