10.3.2 Evaluations During Study

The elements of the ACS assessment will be assessed and recorded every 4 hours (Appendix 3). Note: Time Zero is defined as the initial dose of study drug and the first 24 hour period begins with the first dose. All subsequent doses and study assessments

are scheduled from this time point. The first every 4 hour ACS assessment begins as close as possible to 4 hours after the first dose of study drug and the next routine nursing assessment. The studies required on a daily basis include a CBC and a reticulocyte count. Follow-up blood cultures are obtained at the discretion of the attending physician but should be considered every 24 hours if the subject is persistently febrile (temperature $\geq 38.5^{\circ}\text{C}$). A daily weight, physical exam, and vital signs (every 4 hours which includes blood pressure) will be recorded on the subject's medical record. Subjects will be monitored by continuous pulse oximetry until there has been no requirement for supplemental oxygen for 24 hours and there is clinical improvement. Oxygen saturation (O_2) will be recorded at least every 4 hours with the vital signs until pulse oximetry is stopped. A semi-quantitative, age-appropriate rating of pain intensity [the 0-10 Oucher Scale (age < 10 years) or the 0-10 numeric rating scale (age ≥ 10 years)] will also be obtained by the nurse and recorded with each set of vital signs. A follow-up chest radiograph is not required, but it can be obtained if clinically appropriate. The daily amount and type of opioid analgesia as well as the number and types of transfusions will be recorded. Accurate, cumulative fluid balance measurements (ins and outs) will be recorded every 8 hours on the subject's medical record. AEs will be recorded as they occur throughout hospitalization. The duration of fever, hypoxemia, and hospitalization will also be recorded. Table 10.2 summarizes these evaluations. Furthermore, blood samples will be drawn for the central laboratory measurements at Baseline and Days 1, 2, and 8 (See Table 10.1.).

Table 10.2 Clinical and Clinical Laboratory Evaluations and Procedures

	Inpatient				Inpatient or Outpatient	
	Baseline	Daily	Inter- mittent	Contin- uous	Follow-up #1(7- 10 d) ⁶	Follow-up #2 ⁶
ACS assessment ¹	X		Every 4h		X	X
History	X				Interval ²	Interval ²
Physical exam	X	X				X
Weight	X	X				X
Vital signs	X		Every 4h ⁵		X	X
CBC, reticulocyte count	X	X			X	X
Blood culture	X	X ³				
Chest radiograph	X					X

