13.3 Statistical Considerations

13.3.1 Covariates

Age group and severity group will be used as covariates in the primary analysis. Baseline laboratory measurements will be controlled for when analyzing laboratory outcomes. Center will be included in the models as permitted by sample size. Other covariates may be considered in the analysis of clinical, laboratory, and safety outcomes as needed.

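### The longitudinal pain-score model omits baseline pain, so this secondary comparison is less precise than the collected data allow and more exposed to chance imbalance

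*Protocol*

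**What the plan says.** Section 13.2.2 gives the pain analysis as a "GLMM with treatment, age group, severity, and timepoint as fixed effects and subject as a random effect for the longitudinal pain scores". The longitudinal laboratory model in the same section is fitted "with treatment, baseline measurement, age group, and severity as fixed effects and subject as a random effect". Section 13.3.1 repeats the distinction: "Baseline laboratory measurements will be controlled for when analyzing laboratory outcomes". For everything else that section says only that further covariates may be considered if needed.

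A baseline pain score exists. Section 10.3.1 states: "Immediately after enrolling a subject, the elements of the ACS assessment will be assessed and the following additional assessments performed or measurements taken", and the list that follows includes pain intensity on the Oucher or numeric scale. Table 10.2 also marks the pain scale at baseline. Section 8 defines enrollment as the signing of consent, and Section 9.2 states: "After enrollment, subjects will be randomized to one of two treatment arms". In hospital, the pain rating "will also be obtained by the nurse and recorded with each set of vital signs", which means every 4 hours. Table 10.2 and Section 10.3.3 add a pain assessment at both follow-up visits.

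**The concern.** Section 6.2 predicts that dexamethasone will reduce pain, and pain rating is a listed secondary endpoint. Starting pain can differ widely between subjects: under Section 8.1, chest wall pain is only one of several alternative entry findings. Nothing in the allocation balances it, because minimization in Section 9.2 uses site, age group and severity, and severity in Section 8.3 is defined by saturation, extent of infiltrates and respiratory failure or support.

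The subject random effect does not replace the missing covariate. It accounts for correlation among one subject's ratings, but the between-subject variation stays in the treatment contrast. Part of that variation could be removed with a score the trial already collects.

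A second uncertainty follows from the same omission. The text does not say whether the pre-dose score is one of the model's timepoints. If it is, a rating that treatment cannot have affected is averaged into the treatment effect.

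**Working it through.** **The plan's own figures.** The protocol states no power, standard deviation or precision for pain, so there is no pain figure to reproduce. Its only sample-size figure is for the primary endpoint: 54 per group, or 56 with the allowance for withdrawals. A Satterthwaite t-test with a log-scale difference of 4.25 − 3.95 = 0.30, standard deviations 0.6 and 0.3, and two-sided alpha 0.05 gives 89.5% power at 53 and 90.1% at 54 per group. That figure stands and does not depend on the pain model.

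**Timing of the baseline score.** Sections 8, 9.2 and 10.3.1, read together, place the rating between consent and randomization. They do not state the order of rating and randomization outright. However, Section 10.3.2 takes the first dose as time zero and schedules later assessments from it, so the baseline score precedes treatment and is a legitimate covariate.

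**Assumptions (not in the documents).**
- Correlation ρ between any two of a subject's pain scores, constant over time: 0.3 to 0.5.
- Number of post-dose ratings m: 12, which is 48 hours at one rating per 4 hours. Values of 6 and 18 were also tried.
- Equal m for all subjects and equal variance at each rating.

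**Precision with and without baseline.** For the mean of m post-dose scores, in units of the single-score variance:
- without baseline: V0 = [1 + (m − 1)ρ] / m
- with baseline as covariate: V1 = V0 − ρ²
- standard-error ratio = √(V1 / V0)

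| ρ (m = 12) | V0 | V1 | V1/V0 | SE ratio | SE ratio, simulated |
|---|---|---|---|---|---|
| 0.3 | (1 + 3.3)/12 = 0.358 | 0.358 − 0.09 = 0.268 | 0.749 | 0.865 | 0.864 |
| 0.5 | (1 + 5.5)/12 = 0.542 | 0.542 − 0.25 = 0.292 | 0.538 | 0.734 | 0.736 |

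The simulation used 56 per arm and 4,000 runs. With m = 6 the SE ratios are 0.885 and 0.756; with m = 18 they are 0.857 and 0.725.

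**If correlation fades with time.** Take the correlation at lag k (in ratings) as a + (1 − a)φ^k, and compute V1/V0 as 1 minus the squared correlation between baseline and the post-dose mean. For m = 12:

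| a | φ | V1/V0 | SE ratio |
|---|---|---|---|
| 0.1 | 0.7 | 0.827 | 0.91 |
| 0.2 | 0.7 | 0.746 | 0.86 |
| 0.4 | 0.7 | 0.572 | 0.76 |
| 0 | 0.8 | 0.804 | 0.90 |

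Over m = 6 to 18, these patterns give V1/V0 from 0.503 to 0.874, so SE ratios from about 0.71 to 0.94.

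**Chance imbalance.** With 56 per arm, the standard error of the baseline difference is √(2/56) = 0.19 of a single-score standard deviation. Under constant correlation, a fraction ρ of a baseline difference carries into the unadjusted post-dose comparison. A one-standard-error imbalance therefore shifts it by 0.3 × 0.19 = 0.06 to 0.5 × 0.19 = 0.09 standard deviations.

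**If the pre-dose score is kept as a response.** Without a treatment-by-timepoint term, the treatment effect averages m affected ratings and one unaffected rating, so it shrinks by m/(m + 1): 6/7 = 0.86, 12/13 = 0.92, 18/19 = 0.95.

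**The case against.** The strongest case on the other side is that the listed model is a valid randomized comparison and states nothing false. Section 13 defers detail to a statistical analysis plan, and Section 13.3.1 lets other covariates be considered for clinical outcomes. This stands in part: the protocol permits baseline pain. But it lists this model's fixed effects and leaves baseline out. A covariate added only as needed, possibly after an imbalance is seen, lacks the protection of prespecification.

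The laboratory contrast is also not like for like. That model is for change from baseline, where a baseline covariate is a usual companion, while the pain model is for the scores themselves. The difference alone therefore does not prove an inconsistency. The precision argument does not rely on it.

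Age group and severity are in the model and may absorb some variation in starting pain. That is fair, and it moves the real gain toward the smaller end.

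A reader might go further and infer several things that the documents do not support:
- *That pain ratings end at discharge, so baseline is needed to make missing-at-random credible.* Only the 4-hourly series ends there; both follow-up visits require a pain assessment. The mixed model also already uses all observed in-hospital scores.
- *That baseline is the strongest predictor of later pain.* No section gives evidence on this.
- *That imbalance passes into the estimate in full.* It does so only in proportion to the correlation.
- *That the loss converts to a number of subjects through 1/(1 − ρ²).* That formula is for a single follow-up score, not for repeated ratings with a subject effect.

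**Conclusion.** The point holds as a minor efficiency matter. The pain model omits a covariate that is already collected before treatment and is not balanced by the allocation. Under a constant correlation of 0.3 to 0.5 and 12 post-dose ratings, including it would bring the standard error to about 0.87 to 0.73 of its unadjusted value. Under the decaying patterns tried, the ratio lies between about 0.71 and 0.94 over 6 to 18 ratings. All of these figures rest on assumed correlations, and the one that matters is what remains after age group and severity.

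It would be wrong to read this as systematic bias: randomization protects the unadjusted comparison apart from chance imbalance. The exception is the reading in which the pre-dose score is a response, which would pull the treatment effect toward zero by m/(m + 1). The text does not say that this is intended. Under Section 13.3.3 all p-values other than the primary are descriptive. The primary test and the 54 or 56 per group are untouched.

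**What to change.** In Section 13.2.2, add the baseline pain score as a fixed effect in the pain model and state that only post-dose scores are responses. In Section 13.3.1, name baseline pain alongside the baseline laboratory values as a prespecified covariate. A treatment-by-timepoint term is optional and is not needed for this point.

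The cost is one model term and a sentence in each section, settled before unblinding. No new data, visits or subjects are required.
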